Midodrine hydrochloride [d,1-alpha-(2'5'-dimethoxyphenyl)-β-(glycinamidoethanol); C12H19N2O4Cl] is a pro-drug that undergoes enzymatic hydrolysis in the systemic circulation to form the active metabolite desglymidodrine; midodrine is nearly completely absorbed after oral administration, even in models of NOH in which gastroparesis is common. It has been shown that midodrine does not cross the blood brain barrier; therefore, it is not associated with central nervous system effects. A few relatively small multi-center, randomized placebo-controlled clinical trials have been conducted to determine the efficacy of midodrine to treat symptomatic OH in various models of autonomic failure (Bradbury-Eggleston [pure autonomic failure], Shy-Drager syndromes [multiple system atrophy], Parkinson's disease and diabetic neuropathy). Compared to placebo, 10 mg midodrine TID increased standing BP and improved symptoms of dizziness or light-headedness during standing. Of note, two reports suggest that midodrine improves subjective reporting of energy level and depression.

[figure not shown]
Although our data indicate that between 39% and 70% of the SCI population is hypotensive, less than 1% of veterans with SCI is diagnosed or prescribed treatment for this condition. Disparity between the prevalence of hypotension and the diagnosis in the SCI population is disturbing because of the possible deleterious effects on cognitive function, mood and QOL; adverse effects which may be magnified in individuals with a long-term physical disability. Further, although these individuals do not complain of symptoms, a recent report found significantly increased incidence of ischemic stroke in the Taiwan's SCI population compared to age-, sex- and propensity-matched controls, which may relate to persistent cerebral hypoperfusion, secondary to systemic hypotension.

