about 60 minutes to complete and HR, BP, and CBF will be monitored and recorded during this testing. After the NP battery is complete, subjects will be asked to answer questions related to how BPD impacts their mood and QOL (Appendix 8); these short form questionnaires were developed for use in the SCI population and will take about 15-minutes to complete. In addition, to scales developed for use in the SCI population, because fatigue was ranked highest in terms of the adverse impact of hypotension on QOL by subjects with SCI from our focus group sessions (Figure 4), we will assess fatigue specifically using the PROMIS short form and the fatigue severity scale (Appendix 8). Finally, subjects will be equipped with a 24-hour BP monitor, and will be sent home with a log to record their activities of daily living (ADL) in association with the BP recordings (Appendix 9). In addition, subjects will be sent home with a 24-hour urine collection contained and will be asked to empty their leg bag, or to urinate into this contained at each voiding for a 24-hour period to assess hydration status. Post-randomization testing will be scheduled for approximately  $30\pm3$  days after randomization and, prior to returning to the laboratory, subjects will be asked to take their morning dose of the study medication. These visits will take about 4 hours.

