**Treatment Phase** –After pre-randomization testing, subjects will be randomized to either midodrine (at the individually effective dose) or matching placebo and will be sent home with a one-month ( $30\pm3$  day) supply. Subjects will be asked to take the study medication three times per day, at approximately 8 am, 12 noon and 4 pm; however, each patient will establish his/her daily regimen with [name] based on their individual sleep/wake schedules and ADLs. Subjects will be asked to keep a log of the time of day each dose was taken along with their BP and any adverse events (Appendix 10). Three BP values will be recorded and uploaded directly to [www.HealthVault.com](http://www.HealthVault.com) at the time of dosing and 1 hour after taking each daily dose (total of 18 BP entries daily). Only study investigators will have access to; this website, which will be password protected and the data will be stored behind the VA firewall. Study investigators will review daily BP entries and will contact the subject if data are missing or if there is evidence of a hypertensive episode. Subjects will be asked to report, immediately (within 1 hour), any significant AE, and study investigators will contact each subject weekly to discuss study specific information and general health and wellbeing. If an individual develops a fever or any other symptom of an acute illness or infection they will be taken off study medication and discontinued from participation and will be encouraged to visit their primary care physician for an evaluation. If after treatment of the illness or infection the subject is cleared for participation by the treating physician he/she may resume participation beginning with pre-randomization testing.

**Interim Visit** : Subjects will be asked to return to the laboratory approximately 10 days after randomization, in the late morning or early afternoon, after taking their scheduled daily dose for assessment of BP, HR and CBF and AE reporting. This visit will take about 2 hours.

**Follow -up Visit** – A follow-up visit will be scheduled 7 to 10 days after completion of the Treatment Phase to collect information on any AE(s) experienced after discontinuation of study medication and for a final laboratory assessment of HR, BP and CBF. This visit will take about 2 hours.

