- Analysis of covariance (ANCOVA) will be used to determine the change in CBF at rest and during cognitive testing following randomization to midodrine versus placebo. Pre-randomization CBF will be used as the covariate. Our hypothesis is that there will be a significant increase in CBF, both at rest and during cognitive testing, after 30-days treatment with midodrine compared to placebo.

Memory and Attention Processing :

- ANCOVA will be used to determine the change in cognitive function from baseline to post-treatment following randomization to midodrine versus placebo, using the pre-randomization t-score as the covariate. Our hypothesis is that there will be a significant improvement in cognitive function in individuals treated with midodrine as assessed by standardized cognitive tests of memory and attention & processing speed compared to those randomized to placebo.

Depression, Anxiety and Fatigue :

- ANCOVA will be used to determine the change in mood and QOL score from baseline to post-treatment following randomization to midodrine versus placebo, using the pre-randomization QOL score as the covariate. Our hypothesis is that there will be a significant improvement in QOL in individuals treated with midodrine as assessed by the BPQOL compared to those randomized to placebo.

Adverse Events Reporting :

- To determine the differences in AEs reported at the end of 30-days treatment following randomization to midodrine versus placebo. Our hypothesis is that there will be an increase in mild and moderate drug-related AEs in individuals treated with midodrine compared to those on placebo. A few AE's may be expected to include supine hypertension (may not have been present prior to drug **administration**), **exacerbation of AD (elevated BPs recorded during known trigger's for AD, such as bowel care, bladder distension, transfers), pruritis, urinary retention and more severe or more frequent headaches.**

Secondary Analyses :

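### As written, the mood analysis is adjusted only for baseline QOL, and the two fatigue scales collected are named in no analysis

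*Combined protocol and SAP*

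**What the plan says.** The Study Objectives section has a block headed *Depression, Anxiety and Fatigue*. Its analysis sentence reads "ANCOVA will be used to determine the change in mood and QOL score from baseline to post-treatment", by randomized group, "using the pre-randomization QOL score as the covariate". Its single hypothesis reads: "there will be a significant improvement in QOL in individuals treated with midodrine as assessed by the BPQOL compared to those randomized to placebo". The block names no depression, anxiety or fatigue scale.

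The data collection is described under *Pre- and Post-Treatment Visits* in Research Design and Methods. After the neuropsychological battery, "subjects will be asked to answer questions related to how BPD impacts their mood and QOL". The investigators then add two instruments because "fatigue was ranked highest in terms of the adverse impact of hypotension on QOL by subjects with SCI": "we will assess fatigue specifically using the PROMIS short form and the fatigue severity scale". All of these are collected before randomization and again at about day 30, so a baseline exists for every scale.

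**The concern.** There are two gaps between what is collected and what is analysed.

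- **Covariate.** The outcome is mood and QOL, but the covariate is QOL alone. An analyst who follows the text would leave each mood scale unadjusted for its own starting value and would lose precision that the data already provide.
- **Fatigue.** The word stands in the block heading and the protocol gives a reason for measuring it twice. Yet neither scale has a named analysis, covariate or status.

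The trial's primary objective is to produce effect sizes for CBF, cognition, mood and QOL that can power a larger study. The residual SD and adjusted difference for each scale are therefore the product of the pilot. If the model and the list of scales are unclear, those figures are less precise than they need be, and the choice of which scales to report is left until the data are in.

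**Working it through.** **1. The plan's own figures.** The target is 20 per arm, so 40 in all, with about 10% attrition: 40 × (1 − 0.10) = 36 completers. This matches the stated figure and gives 18 per arm if losses are equal. The plan gives no alpha, power, SD or effect size for mood, QOL or fatigue.

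**2. The three ANCOVA blocks side by side.**

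| Block | Outcome | Covariate stated | Like for like? |
|---|---|---|---|
| Cerebral Blood Flow | change in CBF | baseline CBF | yes |
| Memory and Attention Processing | change in cognitive function | baseline t-score | yes |
| Depression, Anxiety and Fatigue | change in mood and QOL score | baseline QOL score | QOL yes; mood no; fatigue not named |

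The BPQOL hypothesis itself is correctly adjusted. The gap concerns the mood scales, and the fatigue scales if they are meant to be included.

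**3. Cost of the literal covariate.** Assumptions, none from the documents: each scale has SD 1 at both visits; ρ is a mood scale's pre-post correlation (0.3 to 0.8); r is the correlation of baseline mood with baseline QOL (0 to 0.7); baseline QOL is related to mood change only through baseline mood.

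- Own-baseline ANCOVA, residual variance: 1 − ρ². This is the same whether the outcome is change or the day-30 score.
- Change adjusted for baseline QOL only, residual variance: 2(1 − ρ) − [(1 − ρ)r]².

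| ρ | Own baseline | QOL only, r = 0 | Ratio | QOL only, r = 0.7 | Ratio |
|---|---|---|---|---|---|
| 0.3 | 0.91 | 1.40 | 1.54 | 1.160 | 1.27 |
| 0.5 | 0.75 | 1.00 | 1.33 | 0.878 | 1.17 |
| 0.7 | 0.51 | 0.60 | 1.18 | 0.556 | 1.09 |
| 0.8 | 0.36 | 0.40 | 1.11 | 0.380 | 1.06 |

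The excess runs from 6% to 54%. The r = 0 column is the worst case for each ρ, because a covariate cannot raise the population residual variance. At ρ = 0.7 the ratio is therefore at most 0.60/0.51 = 1.18, and 36/1.18 is about 31 subjects.

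**4. The same in detectable differences.** With 18 per arm, two-sided 0.05 and 80% power (assumed), the detectable difference is (1.960 + 0.842) × √(2/18) × residual SD = 0.934 × residual SD. At ρ = 0.7 this is 0.934 × √0.51 = 0.67 SD with own baseline, against at most 0.934 × √0.60 = 0.72 SD. At ρ = 0.3 it is 0.89 against at most 1.10 SD.

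**5. Why the scales need a stated status.** If each were tested at 0.05 and the tests were independent, the chance of at least one false positive would be 1 − 0.95³ = 14.3% for three scales (BPQOL and two fatigue scales). For five scales (adding one depression and one anxiety scale, an assumed count) it would be 1 − 0.95⁵ = 22.6%.

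**The case against.** The strongest reply is that the covariate wording is shorthand. The section uses one compact form throughout: a single baseline CBF for rest and testing, and a single t-score for several cognitive tests. Read in parallel, the QOL covariate may simply mean each measure's own baseline. That is plausible, and it is why this is a clarification and not a proven error. It does not remove the point, since the text can be followed literally and the clearer wording costs nothing.

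The general ANCOVA sentence, under a heading that includes fatigue, can also be read to cover the fatigue scales. It would therefore be too strong to say that they go unanalysed. What is missing is any explicit statement that they are included, with what covariate and what status. Appendix 8, which holds the questionnaires, is not among the documents supplied, so separate depression and anxiety forms cannot be confirmed or ruled out.

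A reader might infer a larger precision loss. With correlations of 0.7 with own baseline and 0.4 with baseline QOL, (1 − 0.16)/(1 − 0.49) = 1.65, which would make 36 subjects worth about 22. That ratio applies to a day-30 score with no baseline subtracted. The plan analyses change, so the baseline is already subtracted and the bound of 1.18 applies at that correlation.

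**Conclusion.** The point holds as a specification gap with a modest cost. The stated covariate fits QOL but not mood, and the two fatigue scales have no named analysis. The loss for mood is 6% to 54% in residual variance over the assumed correlations, and at most 18% at a pre-post correlation of 0.7. It is nil if the wording was meant as shorthand and is carried out that way.

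A reader might go further on three counts, which the documents do not support:

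- **That the BPQOL is the instrument least able to show change.** The background does say of hypotensive people with SCI that "although these individuals do not complain of symptoms", but being asymptomatic is not an entry criterion. The protocol describes the BPQOL items as validated, though still in field testing, and reports that focus-group participants could readily name areas of life affected by BP dysregulation. A floor effect is not documented and cannot be sized.
- **That a fatigue scale should lead.** This would replace the investigators' hypothesis. The background lists fatigue among the symptoms of hypotension, so the fatigue scales could share any floor.
- **That visible BP readings call for another lead scale or for results split by treatment guess.** It is true that "Subjects will be asked to keep a log of the time of day each dose was taken along with their BP", with 18 entries a day. But knowledge of the readings could colour any self-report, including fatigue, so changing the lead scale would not remove the risk. A day-30 guess is a post-randomization variable that efficacy itself can drive, so results split by it are hard to interpret.

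**What to change.** In the *Depression, Anxiety and Fatigue* block of the Study Objectives section:

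1. List every mood, QOL and fatigue scale that is collected, naming the PROMIS fatigue short form and the fatigue severity scale.
2. State one ANCOVA per scale, with that scale's own pre-randomization score as the covariate.
3. Keep the BPQOL as the hypothesised outcome and label the other scales exploratory, reporting for each the adjusted difference with its confidence interval and the residual SD needed to plan the larger trial.

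The cost is a few lines of text. No new data, visits or subjects are needed, because every baseline is already collected, and the investigators' hypothesis is unchanged.

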## Research Design and Methods

We propose to determine the effects of midodrine, administered in a randomized, double blind, placebo-controlled, outpatient trial to normalize BP over a 30-day period, on CBF, cognitive function, mood and QOL. Our primary objective is to generate pilot data describing the effect size of change in CBF, cognitive test score, mood and QOL following sustained elevation in BP, to normal levels, in hypotensive individuals with SCI.

Approximately 50 subjects with SCI will be screened for study eligibility. We anticipate that approximately 40 of the subjects screened will be eligible and will undergo a 4-hour laboratory dose-effect trial. Once dose has been determined subjects will be randomized by IVAN (Interactive Touch Tone Randomization System) to receive either midodrine or placebo for the 30-day out-patient drug treatment intervention. Randomization will occur in a double-blinded manner, and individuals that use an abdominal binder regularly will be stratified equally as will those with a positive history of traumatic brain injury (TBI). Our recruitment target is 20 subjects per randomization category. We estimate approximately 10% attrition during the 30-day out-patient treatment protocol; as such, complete data will be available in ~36 subjects. Study medication and placebo will be distributed by the James J Peters VAMC Pharmacy Service. The study is proposed to be completed in two years. Total enrollment will be accomplished within 18 months of obtaining full IRB approval, which should be complete within 6 months of funding, and subject participation is estimated to last about 6-8 weeks.

**Eligibility Criteria – Inclusion Criteria:** (1) males and non pregnant females; (2) 18 – 65 years of age; (3) chronic SCI ( $\geq 1$  year post injury); (4) ability to provide informed consent; (5) laboratory or clinical evidence of hypotension (WHO criteria - SBP  $\leq 110$  mmHg in males and  $\leq 100$  mmHg in females). **Exclusion Criteria:** (1) SBP  $> 110$  mmHg for males and  $> 100$  mmHg for females (2) documented history of: (a) coronary artery disease, (b) stroke, (c) diabetes mellitus, (d) current pregnancy or lactation, (e) cardiac arrhythmias; (f) significant systemic, hepatic, cardiac or renal illness, (g) suspected malignancy, (h) neurological disease other

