than SCI; (i) history of frequent and/or severe autonomic dysreflexia (AD)\*; (j) known drug allergy to midodrine; (k) acute current illness or infection (l) psychiatric disorders and (m) substance abuse.

\*The incidence of AD is reported to be between 48-90% during rehabilitation in individuals with tetraplegia and high paraplegia (above T6), and may increase with time post-injury. However, in our review of the medical record, the diagnosis of AD was about 6% of veterans with tetraplegia and high paraplegia (T1-T6), the diagnosis of AD was less than 1% in those with lower thoracic lesions (T7 and below). Because administration of midodrine may worsen BP elevations during episodes of AD, and we cannot rely on the medical record for an accurate report of this condition, we will administer an AD questionnaire (Appendix 4) to all participants, any potential subject with frequent (3+ episodes/week) or severe (BP elevation  $\geq$  150/95 mmHg and/or self-reported adverse symptomology) episodes of AD will be excluded. To evaluate the impact of midodrine on BP elevations during AD, eligible subjects will be sent home with the same survey, modified to include: subject number, the date and the BP readings.

**Screening Visit** – Individuals with SCI will be approached by investigators and asked to provide informed consent to participate in the Screening Phase to determine eligibility. Any subject taking a vasoconstrictor agent will be asked to stop these medications 2 days or 5 half lives (whichever is longer) prior to the screening visit. The screening assessments will include: medical intake information (Appendix 5), medical history (Appendix 6), physical examination, American Spinal Cord Injury Impairment Scale (AIS) classification, clinical symptoms survey for OH and BP monitoring. The BP monitoring will include brachial manual assessments for 10 minutes in the seated and 10 minutes in the supine position and will be recorded each minute. Individuals will be eligible to participate if the average seated or supine recordings meets the WHO criteria and there is no evidence of sustained elevation in BP  $>135/85$  mmHg. This visit will take about 2 hours.

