**Data and Statistical Analysis** – The objectives of this proposed investigation are to determine the effects of normalizing BP for 30-days on with midodrine hydrochloride compared to matching placebo, in hypotensive individuals with SCI, on: 1) CBF at rest and during cognitive testing, 2) cognitive function, 3) mood and QOL, and (4) the number and severity of AE reporting. A similar proposal was submitted to the VA Cooperative Studies Program, but was not funded due to the lack of convincing preliminary data demonstrating that increases in systemic BP, secondary to extended use of midodrine in hypotensive individuals with SCI, raises CBF at rest and during cognitive testing and improves test performance (Appendix 11). Therefore, this project will test the following hypotheses in an effort to provide sufficient and convincing data to support a large -scale clinical trial to determine the long term benefits of normalizing BP in individuals with SCI across multiple VA sites through the VA Cooperative Studies Program.

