- Our conceptual model is that prescription medication class, use of support stockings, abdominal binders and history of TBI may function as mediator variables between SCI and the dependent variables. To explore this mediation, at a first level of analysis we will examine the bivariate relationships between the mediator and dependent variables. Second, we will build hierarchical multiple regression models in which a potential mediator variable and SCI status (dummy coded) are both forced into the model. In addition, examination of the partial correlation between SCI and dependent variables (after partialing out the effect of the mediators relative to the zero order correlation will provide insight into the effect size.

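### The secondary mediation models use SCI status as a predictor, but every participant has SCI, so the SCI terms cannot be estimated as written

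*Combined protocol and SAP*

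**What the plan says.** The last part of the statistical section (Secondary Analyses, under Study Objectives) proposes that medication class, support stockings, abdominal binders and a history of traumatic brain injury (TBI) mediate between SCI and the outcomes. It has three parts:

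- Bivariate relations between each mediator and each outcome.
- Regression: "we will build hierarchical multiple regression models in which a potential mediator variable and SCI status (dummy coded) are both forced into the model".
- "examination of the partial correlation between SCI and dependent variables", set against the zero-order correlation, which "will provide insight into the effect size".

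The trial population is described as follows:

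- Research Design and Methods: "Approximately 50 subjects with SCI will be screened for study eligibility". Chronic SCI of at least one year is an inclusion criterion, and randomisation is to midodrine or placebo.
- Screening Visit: "Individuals with SCI will be approached by investigators and asked to provide informed consent".
- Data and Statistical Analysis: midodrine is "compared to matching placebo, in hypotensive individuals with SCI".

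People without SCI appear only in the Background and the Preliminary Studies, as comparators in other work. None is an arm of this trial.

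**The concern.** A dummy variable for SCI status, and any correlation with SCI, needs participants with and without SCI. This trial has only the former. The regression and correlation parts would make sense in the earlier SCI versus non-SCI studies that the protocol describes, but not here.

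At stake is the second level of the secondary analysis and the effect-size information it is meant to supply. If software silently drops the constant term, a model with one mediator is left with only the mediator-outcome association that the bivariate step already gives. If someone instead substitutes another variable at analysis, the choice could be made after seeing the data.

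**Working it through.** **Inputs.** From Research Design and Methods: 20 randomised per arm, 40 in total; 10% attrition; about 36 with complete data. The plan's own figure reproduces: 40 × (1 − 0.10) = 36. The plan gives no sample size, power or effect size for the mediation models.

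**Coefficient.** Let s = 1 for every participant and m be a mediator. The model is y = a + b·s + c·m + error. Since s = 1 for all, this is y = (a + b) + c·m + error. Only the sum a + b can be estimated, not b. A numerical check with an illustrative binary mediator gave rank 2 for the three columns [1, s, m] at n = 36 and at n = 40. Coding s = 0 for all also gives rank 2 (checked at n = 36).

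**Zero-order correlation.** r = Σ(s − s̄)(y − ȳ) / √[Σ(s − s̄)² · Σ(y − ȳ)²]. Every s − s̄ is 0, so r = 0/0.

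**Partial correlation.** This correlates the residual of s given m with the residual of y given m. A constant s is fitted exactly by the intercept, so its residual sum of squares is 0 and the partial correlation is also 0/0. None of this depends on the sample size or on the simulated mediator.

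**If a characteristic that varies were used instead:**

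| Term in place of SCI status | Rank / columns |
|---|---|
| Two-level injury category | 3 / 3 |
| Three-level category (two dummies), all levels represented | 4 / 4 |
| Randomised arm, 18 v 18 | 3 / 3 |

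**Precision with a two-level or scored characteristic, 36 completers.** The Fisher z standard error is 1/√(n − 3 − k), where k is the number of single-column mediators partialled out. The 95% limits are tanh[atanh(r) ± 1.96 × SE].

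| k | SE | r = 0 | r = 0.3 |
|---|---|---|---|
| 1 | 1/√32 = 0.177 | −0.33 to 0.33 | −0.04 to 0.58 |
| 4 | 1/√29 = 0.186 | −0.35 to 0.35 | −0.05 to 0.59 |

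The plan names four potential mediators, which is why k = 4 is shown. The r values are illustrative. A characteristic with three or more unordered levels has no single partial correlation, so the table does not apply to it.

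**The case against.** The best defence is that SCI status is shorthand for something that does vary. The Preliminary Studies group patients as tetraplegia, high paraplegia and low paraplegia, and the Screening Visit includes the "American Spinal Cord Injury Impairment Scale (AIS) classification". The intake and history forms are appendices that are not shown, and they could hold such a code. Treatment arm might also have been meant. Any of these would give a model that can be fitted.

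That possibility is real, but it does not rescue the text. The Secondary Analyses paragraph refers only to SCI or SCI status, and no visible section redefines it. Lesion level, AIS grade and arm would answer three different questions. Arm fits the stated mediators poorly: regular binder use and TBI history are stratification factors, fixed before treatment, so they cannot mediate its effect.

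Two qualifications stand. First, the regression step merely repeats the bivariate step only if each model holds one mediator. Several mediators entered together would give mutually adjusted associations, though still nothing about SCI. Second, the analysis is secondary and exploratory, which limits the importance of the point.

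**Conclusion.** The concern holds. Read as written, the SCI coefficient and both SCI correlations do not exist in this trial at any sample size. This follows from the eligibility criteria and needs no assumption beyond taking SCI status literally. If an injury category was intended, the model is estimable but undefined in the plan, and the text must still change.

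The consequence is minor. No objective, main hypothesis, sample size or safety analysis rests on this step. The bivariate mediator-outcome step, the relative risk and number needed to treat, and the ANCOVAs are unaffected.

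**What to change.** Before unblinding, do one of the following. The documents do not show whether unblinding has occurred; if it has, label the change post hoc.

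**(a) Redefine the term.** Replace SCI status with a named injury characteristic that varies in this sample, such as lesion level or the AIS grade classified at screening, and list its categories and coding. This makes the model estimable, but does not by itself establish mediation: the plan examines no relation between the exposure and the mediators. Low paraplegia may be sparse, because the preliminary prevalence study found hypotension in 4.42% of that group, against 35.07% in tetraplegia and 26.59% in high paraplegia. Precision would be as tabulated above.

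**(b) Delete the SCI mediation step and its correlations**, and keep the bivariate description. The cost is giving up the SCI-mediation question. If wanted, TBI history and regular binder use can enter as baseline covariates, or as exploratory treatment-by-covariate moderators with confidence intervals, but not as mediators of treatment. Treat stocking use and medication class the same way only if they are recorded at baseline. The visible text does not show this, so it must be confirmed.

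The optional moderator estimates under (b) would be very imprecise. With 18 completers per arm, of whom n1 have the characteristic and n0 = 18 − n1 do not, the interaction SE is √(2/n1 + 2/n0) residual SD. Multiplying by t(0.975, 31 df) gives the 95% half-width; 31 df is 36 less intercept, arm, characteristic, interaction and one baseline covariate.

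| n1 per arm (assumed) | SE | Half-width (residual SD) |
|---|---|---|
| 9 | 0.667 | 1.36 |
| 5 | 0.744 | 1.52 |
| 4 | 0.802 | 1.64 |
| 2 | 1.061 | 2.16 |
| 1 | 1.455 | 2.97 |

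For comparison, the arm effect alone has half-width √(2/18) × t(0.975, 33 df) = 0.68. The n1 values are assumptions, because the documents give no prevalence of binder use or TBI in this sample.

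Either option costs only an edit to the plan.
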